5 PROTOCOL CLARIFICATIONS

In the protocol infections analysis were classified as efficacy analysis. Since this is a real-world study, in this SAP, these analyses will be classified as "Effectiveness analysis" instead of "Efficacy analysis".

In the effectiveness analyses, section 5.3.2 of the protocol, it is planned Poisson regressions for the measure rate of CLABSI and CAUTI/VAP per 1000 central line days with predictors sort of treatment (scrub-the-hub protocol or the disinfecting barrier cap), and variables for the time trend and the unit. In this SAP, it is planned two Poisson regressions for measure rate of CLABSI with all covariables (time trend, unit and sort of treatment). For the second Poisson regression model, since time trend variable and sort of treatment variable are dependent variables, this model will just include sort of treatment and unit. CAUTI and VAP infections

were only collected for the ICU unit/ward, in consequence, Poisson regression models will be performed, if applicable, with time trend and sort of treatment covariables.

Compliance calculation method of the period previous the intervention (scrub-the-hub) and after intervention (prospective period – needleless connectors compliance audits) are presented in section 9 - Data, derivations and transformations.

Infection rates calculation are presented in section 9 - Data, derivations and transformations.

Compliance by format of disinfecting cap (disinfecting cap strips vs. individual disinfecting caps) of the post-intervention period (prospective period) will be assessed. The type of caps used during the study was limited by unit ward. Only ICU unit ward was allowed to use disinfecting barrier cap strips, because of that the ICU post-intervention period compliance and the disinfecting barrier cap strips compliance results will be identical. On the other hand, individual disinfecting caps compliance will be calculated by the other unit wards (2^o floor, 3^o floor, 3^o floor – surgical ward, 4^o floor and 5^o floor). Please see section 9 Data, derivations and transformations.

In the protocol section 5.1 – Datasets Analyzed, CAUTI and VAP data from the six months prior to the intervention will be analyzed and compared to data in the 6-month post intervention recording period to determine product effectiveness. In this SAP, CAUTI and VAP will not be compared between the pre-intervention period and the prospective period, because CAUTI and VAP infections assessments were only collected for ICU unit. Due to the lack of infections assessments in these two periods, only descriptive statistics will be presented.

In the protocol, it is described that the prospective compliance will include the observations of the number of needleless connectors with, and the number of needleless connectors without, disinfecting barriers caps attached. In this SAP for the prospective compliance will include also the observations of applicable ports with misused caps. In section 9 *Data, derivations and transformations* is presented the formula calculation for compliance rate for use of the disinfecting barrier cap on needleless connectors (post-intervention period).

In this SAP the CAUTI and VAP rates will be calculated using the number of CAUTI and VAP variables, instead of CLABSI variables as said in section 5.3.2 Efficacy Analysis of the protocol.

6 DEFINITION OF ANALYSIS SUBSETS

Data from all compliance audits within the six-month recording period (after the first month of intervention) will be analyzed for protocol compliance. This will be compared to compliance

before the intervention, which will be determined by the pre-intervention survey. All surveys from the pre intervention period will be included in the analysis.

CLABSI data from the six months prior to the intervention will be analyzed and compared to data in the 6-month intervention recording period to determine product effectiveness. This analysis will also be performed by MBI (mucosal barrier injury) and not MBI related. CAUTI, and VAP data from the six months prior to the intervention and in the 6-month intervention recording period will be analyzed.

Data from the “implementation and reinforcement” period, first month after the introduction of the intervention, will not be used for the compliance analyses of the primary endpoint and for the effectiveness analysis (secondary endpoints), since this is a training period and may produce bias in the results. However, these data will be summarized using descriptive statistics.

7 STATISTICAL METHODS

All data will be summarized using descriptive statistics namely mean, standard deviation, median, minimum and maximum for quantitative variables and counts and percentages for qualitative variables. Percentages will be calculated based on non-missing values.

All statistical tests will be two-tailed considering a significance level of 5%.

Statistical analysis will be conducted through the software SAS® (version 9.4; SAS Institute Inc, Cary, USA).

7.1 Handling missing data

There will be no imputation of missing data for this study, unless otherwise specified. In case of complete missing dates, date is to be considered as missing.

In case of partial dates, if applicable:

- Missing day is to be considered as the 15th day of the month;
- Missing day and month are to be considered as the 1st day of July.

7.2 Compliance Analyses

Compliance rates to scrub-the-hub disinfection procedures before the intervention will be determined by written survey. The target survey response rate on scrub-the-hub compliance is 70% of healthcare professionals in the intervention wards that utilize needleless connectors for patient IV access. An overall compliance rate and compliance rates per intervention ward will be determined.

The calculation method of the survey compliance rate is presented in section 9 - Data, derivations and transformations. Survey compliance will be assessed by the *scrub time* and *dry time* of the self-reported part of the survey.

Compliance rate for the use of the disinfecting barrier cap on needleless connectors during the intervention recording period will be determined by weekly observations in each assigned intervention ward, which will be scheduled to ensure the absence of a shift bias.

The calculation method of the use of the disinfecting barrier cap on needleless connectors compliance is presented in section 9 - Data, derivations and transformations.

Survey compliance rate and compliance rate for the use of the disinfecting barrier cap on needleless connectors during the intervention recording period by wards will also be assessed.

The Student's t-test for independent samples will be used to compare the compliance rate between pre and post intervention period. In case of no evidence of normality assumptions, the Mann-Whitney U test will be used instead of Student's t-test.

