5.2 Assessment Methods

Compliance

Compliance is defined as following the protocol for disinfection of the needleless connector. In the pre-intervention period, the disinfection protocol will utilize existing institution scrub-the-hub method. Compliance in the pre-intervention period will be determined by survey.

In the intervention period, the disinfection protocol consists of using the disinfecting barrier cap on every needleless connector used for accessing CVC IV lines per protocol. Compliance will be measured using observations by study personnel and/or the principal investigator, according to a schedule to ensure the absence of a shift bias. Observations will take place three times per week during the first four weeks in all intervention wards with a specially designed report form. After the first four weeks, the observations will be scheduled once per week for each intervention ward.

Prospective compliance audits will include observations on the number of needleless connectors with, and the number of needleless connectors without, disinfecting barrier caps attached. The Nurse Assistance Unit will be notified after the end of the audit about any uncapped needleless connectors or misused caps for any necessary corrections. CVCs with connectors that are being used for continuous infusion at the time of the observation will be tallied, but will not be included in the compliance rate calculation.

Infection Rates

Incidence of CLABSI, CAUTI, and VAP will be noted from existing aggregate hospital surveillance system data. The incidence will be recorded for each assigned intervention ward and for intervention ward overall by month, in the six months before the intervention and in the six-month intervention recording period.

3M Confidential

Document Name: CLIN-PROT-ICH-US-05-319980

Clinical and Non-Clinical: CLIN-INDEX-3M-SPON-US-05-014137

[name]

CLABSI is defined as an occurrence of a positive blood culture when a central-line catheter has been in place two days or longer on the date of the event. The rate will be documented in terms of catheter days.

CAUTI is defined as a urinary tract infection where an indwelling urinary catheter was in place for >2 calendar days on the date of event, with day of device placement being Day 1, **AND** an indwelling urinary catheter was in place on the date of event or the day before. The rate will be documented in terms of catheter days.

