2.2 Endpoints

Primary endpoint

The rate of compliance to hub disinfection protocol.

Secondary endpoints

- Rate of central line associated bloodstream infections (CLABSIs) per 1,000 central line days;
- Catheter-Associated Urinary Tract Infection (CAUTI) per 1,000 catheter days and Ventilator-Associated Pneumonia (VAP) per 1,000 ventilator days (controls).

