9 DATA, DERIVATIONS AND TRANSFORMATIONS

- **Scrub-the-hub survey compliance (retrospective period)**

Compliance of the scrub-the-hub (self-reported and coworkers) survey will be calculated through scrub time and dry time:

In each of the scrub time (Table 1) and dry time (Table 2) questions tables a calculation has to be made to provide the percent of the time that the clinician scrubs the hub (Table 1) 10 seconds or more or allows the hub to completely dry (Table 2).

Each answer has a percentage assigned for the calculation of compliance: “Always” = 100%; “Usually” = 75%; “Sometimes” = 25%; and “Never” = 0%.

Only the answers of “≥10 - <15 seconds” and “≥15 seconds” will be considered for the calculation of compliance, because physicians will only be compliant if scrub time is equal or more than 10 seconds. Therefore, in compliance calculation, scrub time for “No scrub”, “<5 seconds”, “≥5 - < 10 seconds” will be multiplied by zero.

For the example bellow (Table 1), compliance of scrub time will be calculated as follow:

$$\begin{array}{r}
 0\% \times 0 \\
 + 25\% \times 0 \\
 + 75\% \times 0 \\
 + 25\% \times 1 \\
 + 0\% \times 1 \\
 \hline
 25\%
 \end{array}$$

The first three rows values would then be multiplied by zero and the last two multiplied by 1. The percentage will then be totaled by summing all the percentages for each scrub time.

Table 1 – Scrub-the-Hub survey (scrub time table)

Scrub Time	Always (100%)	Usually (75%)	Sometimes (25%)	Never (0%)
No scrub				
<5 seconds				
≥5 - <10 seconds				
≥10 - <15 seconds				
≥15 seconds				
If scrub time <10 seconds, indicate the most likely reason:		 The patient urgently needed the medication  High patient - nurse ratio  In my mind, I believe <10 seconds is more than necessary  Another reason: _____		

For dry time, compliance will be calculated as follow:

$$\begin{array}{r}

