 75\% \times 0 \\
 + 25\% \times 1 \\
 \hline
 25\%
 \end{array}$$

The first-row value would then be multiplied by zero and the last row multiplied by 1. The percentage will then be totaled by summing all the percentages for the two dry times.

Table 2 – Scrub-the-Hub survey (dry time table)

Dry Time	Always (100%)	Usually (75%)	Sometimes (25%)	Never (0%)
No dry				
Completely dry				

The total compliance for each physician will be calculated through the following formula:

$$\begin{aligned} \text{Scrub – the – hub survey compliance (\%)} \\ = \text{Scrub time compliance (\%)} \times \text{Dry time compliance (\%)} \end{aligned}$$

For the previous example, scrub-the-hub survey compliance rate was: 25% X 25%= **6,25%**

If missing data are present in scrub-the-hub survey, compliance will not be calculated for that subject.

Compliance rate will be calculated per physician.

- **Compliant clinician in scrub-the-hub survey (target compliance rate achieved)**

A dichotomous variable (yes/no) will be calculated.

Yes – clinician who meet compliance rate equal or higher than 70% in scrub-the-hub survey.
No – Otherwise

- **Compliance rate for use of the disinfecting barrier cap on needleless connectors (post-intervention period)**

The following formula must be considered for each shift and ward:

$$\begin{aligned} \text{Compliance rate for use of disinfecting barrier cap on needleless connectors (\%)} = \\ = \frac{\text{No. of applicable capped ports (correctly used)}}{\text{No. applicable capped ports (correctly used)} + \text{No. applicable uncapped ports} + \text{No. applicable ports with missed caps}} \times 100 \end{aligned}$$

If missing data are present in data compliance audits, for a shift/ward then that compliance will not be calculated for that shift/ward.

- **CLABSI rate per 1000 catheter/days**

The following formula must be considered:

$$\begin{aligned} \text{CLABSI rate per 1000 catheter line/days} \\ = \frac{\text{Number of CLABSIs infections}}{\text{Number of central venous catheter (CVC) days}} \times 1000 \end{aligned}$$

- **CAUTI rate per 1000 catheter/days**

The following formula must be considered:

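### The primary compliance comparison pools variances across two differently built scores, with no provision for unequal spread in either the t-test or its rank-test fallback

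*SAP*

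**What the plan says.** The primary endpoint in SAP 2.2 is "The rate of compliance to hub disinfection protocol". SAP 7.2 states that the Student's "t-test for independent samples will be used to compare the compliance rate between pre and post intervention period". The next sentence adds the only alternative: "In case of no evidence of normality assumptions, the Mann-Whitney U test will be used instead of Student's t-test". SAP 7 sets the level: "All statistical tests will be two-tailed considering a significance level of 5" percent. No variance check and no unequal-variance version of the test is mentioned.

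SAP 9 defines the two quantities being compared.
- **Before:** "Each answer has a percentage assigned for the calculation of compliance", namely 100, 75, 25 or 0. The two scrub-time rows of 10 seconds or more are summed, and the sum is multiplied by the dry-time score. "Compliance rate will be calculated per physician".
- **After:** correctly capped ports divided by all applicable ports. "The following formula must be considered for each shift and ward".

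On audit frequency, Protocol 5.2 says: "After the first four weeks, the observations will be scheduled once per week for each intervention ward". For the survey there is a 70% target response rate but no number of staff.

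**The concern.** The pooled-variance t-test has the right standard error only if the two SDs are equal or the two sample sizes are equal. The plan secures neither. A person's score built by multiplying coarse answers can range over the whole scale, whereas a proportion averages over several ports and tends to vary less. The number of respondents depends on staffing and response, and the number of audits on the calendar.

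If the group with the larger SD is also the smaller group, the pooled standard error is too small and false positives rise. If it is the larger group, the standard error is too large and power is lost. This test is the only between-period comparison of the primary endpoint that SAP 7.2 names.

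**Working it through.** The documents give no SD, expected compliance, survey size or audit count, so there is no planned figure to reproduce. The check shows how far the error rate can move under stated assumptions.

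**Number of audits (inferred).** SAP 5 and 9 list six wards: the ICU and five others. Six months is about 26 weeks, and audits are weekly per ward: 6 × 26 = 156.

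**Survey SD (assumed 30-35 points).** Let each answer be equally likely to be 0, 0.25, 0.75 or 1. Its mean is 0.5 and its mean square is (0 + 0.0625 + 0.5625 + 1)/4 = 0.40625.
- One scrub row times dry time: SD = √(0.40625² − 0.25²) = √0.1025 = 0.32, or 32 points.
- SAP 9 sums two scrub rows. Excluding answer pairs that total more than 100%, the SD is 34 points. Allowing them, it is 53.

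Equally likely answers are only an illustration. Answers bunched near 0 or 100 would give a smaller SD.

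**Audit SD (assumed 10-15 points).** With 10 ports, √(0.8 × 0.2/10) = 12.6 points and √(0.9 × 0.1/10) = 9.5 points. With 4 ports at 80% it is √(0.8 × 0.2/4) = 20 points, so SDs of 25 and 20 were also tried.

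**Formulas.** Subscript 1 is survey and 2 is audit.
- Pooled variance: sp² = [(n1−1)s1² + (n2−1)s2²]/(n1+n2−2)
- Pooled SE = √[sp²(1/n1 + 1/n2)]; true SE = √(s1²/n1 + s2²/n2)
- R = pooled SE / true SE; actual two-sided error rate = 2[1 − Φ(1.96R)]

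**Example: 60 respondents, SDs 35 and 10.**
- sp² = (59 × 1225 + 155 × 100)/214 = 410.2
- Pooled SE = √[410.2(1/60 + 1/156)] = 3.08
- True SE = √(1225/60 + 100/156) = 4.59
- R = 0.67; error rate = 2[1 − Φ(1.31)] = 19%

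**Actual error rate of the nominal 5% pooled test, 156 audits:**

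| SDs (survey/audit) | 60 respondents | 100 | 156 | 300 |
|---|---|---|---|---|
| 35/10 | 19% | 10.5% | 5.0% | 1.0% |
| 30/15 | 14% | 8.6% | 5.0% | 1.8% |
| 25/20 | 7.6% | 6.2% | 5.0% | 3.6% |
| 10/30 (order reversed) | 0.4% | 1.9% | 5.0% | 13% |

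With equal SDs the rate is 5% at every sample size. If each weekly audit gave three shift rows (3 × 156 = 468, a further assumption), 100 respondents would give 29% with SDs 35/10 and 19% with 30/15.

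**Simulation check** (normal data, equal means). With 156 audits and SDs 35/10, the pooled test rejected in 23%, 10%, 5.5% and 0.9% of runs at 50, 100, 156 and 300 respondents. Over all scenarios simulated, Welch's test rejected in 4.8-5.4%.

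**The fallback.** Illustrative discrete survey scores (30 to 200 respondents) and audit proportions (156 audits) failed a Shapiro-Wilk test in every simulated sample. The SAP names no normality test, so this shows what is probable, not what will happen. With SDs 35/10, Mann-Whitney rejected equal-mean normal data in 13%, 9.7%, 7.0% and 3.2% of runs at 50, 100, 156 and 300 respondents. It responds to differences in distribution generally, so with two differently shaped scores it can reject when mean compliance is the same.

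**The case against.** A reader might infer that the spreads must differ widely, that the direction of the error follows from the sample sizes alone, and that the planned p-value is therefore wrong. The documents do not support this. They give no SD, survey size, audit count or ports per audit. Protocol 5.2 leaves continuous-infusion connectors out of the rate, which shrinks denominators and widens the audit SD. The table shows that reversing the SDs reverses the direction, that moderate inequality costs little, and that equal group sizes remove the problem.

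The strongest objection is that the t-test would probably not be run, because the normality switch would replace it. This is fair, and it means that changing only the name of the t-test would miss the likely operative test. It does not rescue the plan, since the fallback also departs from 5%.

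Two further points stand. SAP 7.2 says that ward rates will be assessed but does not say that they will be tested, and its text specifies no confidence interval (the table shells are a separate document not seen here). The error may also not change the conclusion. For an assumed 50% against 85% (SDs 35 and 12, 50 respondents, 156 audits), t is 10.7 pooled and 6.9 by Welch. For 70% against 80% (SDs 30 and 15, 100 respondents), it is 3.5 and 3.1. Both tests reject in each case. Precision still differs: in the first case the implied standard errors are 35/10.7 = 3.3 and 35/6.9 = 5.1 points.

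**Conclusion.** The concern holds in conditional form. SAP 7.2 names a pooled-variance test for the primary endpoint, makes no provision for unequal variance, and applies it to two scores whose construction makes unequal spread likely. With survey SD 30-35, audit SD 10-15 and 156 audits, the error rate is about 14-19% at 60 respondents, 9-10% at 100, 5% at 156 and 1-2% at 300. With SDs 25 and 20 it is about 6% at 100. The SDs and survey sizes are assumptions and the audit count is inferred. All these figures treat observations as independent. The fallback test does not remove the problem. The change is worth making because it is cheap and concerns the primary endpoint, but the documents do not show that the trial's conclusion would turn on it.

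**What to change.** In SAP 7.2:
- Prespecify Welch's unequal-variance (Satterthwaite) t-test for the overall pre/post comparison.
- Report the difference in mean compliance with its Welch 95% CI.
- Remove the normality-triggered switch and keep Mann-Whitney as a sensitivity analysis only.
- Use the same method for any ward-level comparison that is made.

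The cost is a short rewording of SAP 7.2, since the standard SAS t-test procedure already gives the Satterthwaite result. If the variances turn out equal, the loss of degrees of freedom is negligible. Stating the choice in advance also prevents a later choice between pooled and unequal-variance p-values. The change does not deal with repeated audits within the same six wards, or with comparing self-report against direct observation. Those need separate treatment, and until then the Welch interval should not be read as accounting for them.

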7.3 Effectiveness Analyses

7.3.1 CLABSI

The statistical analysis for effectiveness is a Poisson regression with outcome measure rate of CLABSI per 1,000 central line days and with predictors sort of treatment (scrub-the-hub protocol or the disinfecting barrier cap), unit (ward) and time trend.

This analysis will also be performed by CLABSI infections associated with mucosal barrier injury (MBI) and not MBI-related.

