5.3.2 Efficacy Analyses

CLABSI

The statistical analysis for efficacy is a Poisson-regression with outcome measure rate of CLABSI per 1,000 central line days and with predictors sort of treatment (scrub the hub protocol or the disinfecting barrier cap), and variables for the time trend and the unit.

CAUTI/VAP

The statistical analysis for efficacy is a Poisson-regression with outcome measure rate of CLABSI per 1,000 central line days and with predictors

[name]

sort of treatment (scrub the hub protocol or the disinfecting barrier cap), and variables for the time trend and the unit.

[CLIN-PROT-ICH-US-05-319980](#), version 8, update to document (Protocol Amendment 2): Protocol amended to document addition of an ad-hoc analysis of CLABSI infections both pre- and post-intervention. CLABSI infections will be further classified as those associated with mucosal barrier injury (MBI), and those that are not MBI-related, using the current CDC NHSN definition of mucosal-barrier injury laboratory-confirmed bloodstream infection (MBI-LCBI). The analysis of the classified CLABSI infections (MBI and not MBI related) will be conducted separately using the same planned analysis as the overall aggregated CLABSI infections.

6. Data Handling and Record Keeping

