8.3 Infection assessments for the pre and post intervention period

The results regarding the infections assessments in the retrospective period (scrub-the-hub) and in the prospective period (use of the disinfecting barrier cap on needleless connectors) will be presented in tables 3 and 4 and listing 5 of the appendix.

CLABSI/CAUTI/VAP comparisons between pre-intervention and prospective periods will be presented in table 5 of the appendix.

Poisson regression results model for predicting rate of CLABSI infections, and by MBI, will be presented in table 6, table 7, table 8, table 9, table 10 and table 11 of the appendix.

Poisson regression results model for predicting rate of CAUTI infections will be presented in table 12 of the appendix.

Poisson regression results model for predicting rate of VAP infections will be presented in table 13 of the appendix.

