10 APPENDIX

External document: CUROS TLFs Version No. 2.0, 03Apr2019

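### The CLABSI Poisson model is incompletely specified: the SAP states no count response, no line-day exposure and no overdispersion allowance

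*SAP*

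**What the plan says.** SAP 7.3.1 specifies a "Poisson regression with outcome measure rate of CLABSI per 1,000 central line days and with predictors sort of treatment", plus ward and time trend, and repeats the analysis for MBI-related and other CLABSIs. Protocol 5.3.2 has the same core wording: "Poisson-regression with outcome measure rate of CLABSI per 1,000 central line days".

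SAP 5 says "it is planned two Poisson regressions for measure rate of CLABSI with all covariables", then drops the trend from the second: "this model will just include sort of treatment and unit". SAP 8.3 describes the output tables as "Poisson regression results model for predicting rate of CLABSI infections, and by MBI".

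Line days serve as the denominator of the rate in the endpoint definitions (Protocol 3.1, SAP 2.2), in Protocol 5.2 and in the SAP 9 formula ("Number of central venous catheter (CVC) days"). No section makes them an exposure, offset or weight in a model. Neither document mentions overdispersion, a scale parameter, a negative binomial model or robust standard errors.

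The SAP does not state the regression row. Protocol 5.2 does say how the data are recorded: "The incidence will be recorded for each assigned intervention ward and for intervention ward overall by month". The table shells are cited only as "External document: CUROS TLFs Version No. 2.0, 03Apr2019".

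**The concern.** A Poisson model takes the variance of its response to equal the mean. That can be reasonable for a count of infections. It is not reasonable for a rate per 1,000 line days, whose precision depends on how many line days lie behind it. A rate of 5 from 200 line days is one infection; the same rate from 2,000 line days is ten. A model given only the rate treats the two alike.

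The second gap remains under any reading. Plain Poisson errors assume no variation beyond chance between months within a ward. Some extra variation is plausible here: catheter types are mixed, and infections in dialysis patients who receive no cap are still counted (Protocol 3.2.1 and 3.2.2).

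At stake are the confidence interval and p-value for the cap effect on CLABSI, a secondary endpoint and the subject of the second project objective. Both SAP 5 models and the MBI split are affected.

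**Working it through.** The plan gives no event count, base rate, line-day total or power figure, so there is nothing of its own to reproduce.

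**Inputs from the documents.** Six units (ICU plus five wards, SAP 5); six months before against six months of recording (SAP 6); two-sided 5% (SAP 7).

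**Assumptions.** Line days per ward-month, a base rate of 5 per 1,000 unless stated, and the variance-to-mean ratio. *Level* below means the true rejection rate of a nominal 5% test when the cap has no effect.

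**1. Literal fit, equal line days D per row.** The true variance of a rate r per 1,000 is r × 1000/D; the model assumes r. So literal SE / correct SE = sqrt(D/1000), and the level is 2 × (1 − Φ(1.96 × ratio)).

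| D per row | SE ratio | Level |
|---|---|---|
| 200 | 0.447 | 38.1% |
| 500 | 0.707 | 16.6% |
| 1,000 | 1.000 | 5.0% |
| 2,000 | 1.414 | 0.6% |

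Simulation (2,000 runs per setting) gave 39.9%, 16.0%, 5.3% and 0.5% with trend, and 38.8%, 16.4%, 5.4% and 0.5% without. Counts with a log(line-days) offset gave 4.2-5.8%.

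**2. Literal fit, unequal wards** (assumed 1200/400/400/300/300/200 line days). Replace D by sum(rate)/sum(rate/D):
- common rate: 6/0.0175 = 343, level 25%
- rate 15 in the largest ward, 2 elsewhere: 25/0.04583 = 545, level 15%
- rate 15 in the smallest ward, 2 elsewhere: 25/0.100 = 250, level 33%

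**3. What this does to an interval.** Assume 36 ward-months per period at 300 line days each, with 54 against 27 infections (rate ratio 0.50).
- Offset: SE = sqrt(1/54 + 1/27) = 0.236, 95% CI 0.32-0.79.
- Literal, rates 5 and 2.5: SE = sqrt(1/(36×5) + 1/(36×2.5)) = 0.129, 95% CI 0.39-0.64.

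Halving the line days (27 against 13.5 expected infections) raises the offset SE to 0.333 and leaves the literal SE at 0.129.

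**4. Offset used, overdispersion present.** With variance-to-mean ratio φ, the plain SE is too small by sqrt(φ), so the level is 2 × (1 − Φ(1.96/sqrt(φ))).
- φ = 1.5: 1.96/1.225 = 1.600, level 11%
- φ = 2: 1.96/1.414 = 1.386, level 17%

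Simulation at 500 line days gave 10.1-11.3% and 16.2-17.6%. Pearson-scaled errors gave 4.8-5.6% and 5.5-6.6%.

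**5. Sparse subsets.** With 0.2 expected infections per row and a trend term, Pearson scaling ran at 7.3% (φ = 1) and 9.5% (φ = 1.5).

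**The case against.** The strongest reply is that Poisson regression of a rate is ordinary shorthand for a count with an offset. SAP 9 builds the rate from infections and CVC days, and the wording of SAP 8.3, which speaks of predicting a rate, suits an offset model. That reading is at least as likely as the literal one, so the results in steps 1 to 3 are conditional. The unseen table shells might also settle it. What stands is that neither the protocol nor the SAP text states the model, although SAP 1 gives clarifying the protocol as one of the SAP's purposes.

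The unstated row is a small gap. On ward-period totals, trend and treatment would be perfectly collinear, so the trend model needs finer rows, and Protocol 5.2 records by ward and month. Ward-month is the natural inference.

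Nothing in the documents shows that overdispersion will occur, and ward and trend terms may absorb part of it. That is a reason to estimate it, not to assume it is absent.

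A reader might infer that the SAP plans a wrong model, or that it will produce false positive CLABSI findings. The documents support neither. They leave the model open, and even a literal fit errs in the conservative direction when rows hold more than 1,000 line days.

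**Conclusion.** The point holds as an incomplete specification that should be corrected before analysis. Read literally, the stated rule gives standard errors that ignore line days, off by sqrt(D/1000) in either direction when rows are equal. Read as shorthand for an offset, it still lacks a dispersion allowance, with a true level of about 10-17% at assumed ratios of 1.5 to 2, against about 5-7% Pearson-scaled.

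All magnitudes are illustrative. The assumed line days alone move the literal-fit level from 0.6% to 38%, so the size and direction in this trial are not known. The primary endpoint, compliance, is unaffected, and neither document ranks CLABSI above the other secondary endpoints. Confidence is medium, because the intended model cannot be confirmed.

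**What to change.** In SAP 7.3.1, for both SAP 5 models and the MBI and non-MBI analyses, state:
- row: ward-month
- response: number of CLABSIs, log link
- offset: log(CVC days)
- a prespecified dispersion allowance, for example Pearson-scaled standard errors with the dispersion estimate reported (negative binomial or robust errors would also serve)
- result: rate ratio with 95% CI

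Keep the rate per 1,000 for descriptive tables.

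**Cost.** SAP wording and standard software options; SAP 9 already uses the counts and CVC days. Intervals may widen. In simulation with assumed wards of 150-400 line days, a true rate ratio of 0.5 and no trend term, Pearson scaling changed power from 74.7% to 73.7% without overdispersion. With gamma overdispersion (k = 0.5) power fell from 70.7% to 60.5%, but there the plain test's level was 11.2%. Pearson scaling should use ward-month rows: on 12 ward-period totals with a normal reference it ran at 10.3%. It can still run at about 7-10% in very sparse MBI subsets, which should be acknowledged.

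**Separate point, same edit.** One paragraph of SAP 5 limits CAUTI and VAP to descriptive statistics. Another allows models where applicable, and SAP 7.3.2 and 8.3 plan them. Reconcile these. If models are kept, replace central line days in SAP 7.3.2 with the urinary catheter days and ventilator days of SAP 2.2 and SAP 9, entered as log offsets.
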